6.4.2. Dose-Limiting Toxicities

Patients are to receive at least 75% of the planned SL-901 doses in C1 and complete study assessments through C2D1 to be eligible for DLT evaluation, unless discontinuing due to DLT. Patients who receive <75% of the planned SL-901 doses in C1 and/or discontinue before completing study assessments through C2D1 for reasons other than DLT are to be replaced.

Toxicities are to be assessed by the Investigator according the NCI CTCAE, v5.0 (available at:

https://ctep.cancer.gov/protocoldevelopment/electronic_applications/docs/CTCAE_v5_Quick_Reference_5x7.pdf.

A DLT occurring during the Run-in PK period or in C1 is defined as any of the following AEs for which there is a reasonable possibility that SL-901 caused the event. (Note that while causality of an AE is to be determined by the Investigator, the Sponsor's assessment of causality can be used to override an Investigator's designation of 'unrelated'; however, the Sponsor's assessment cannot be used to reverse an Investigator's designation of 'related' for the purpose of DLT determination.

- Any \geq Grade 3 non-hematologic AEs, with the exceptions of:
 - Grade 3 nausea, vomiting, diarrhea, constipation, fever, fatigue, or skin rash that resolves to Grade <3 within 72 hours.
 - Grade 3 laboratory abnormalities that are not associated with symptoms and resolve to Grade 1 or baseline by C1D28 (unless otherwise specified).
- Grade 4 thrombocytopenia or Grade 3 thrombocytopenia with $>$ Grade 1 bleeding or requirement for platelet transfusion.
- Grade 4 neutropenia lasting >5 days.
- Febrile neutropenia (ANC $<1\times10^9/L$ with fever $\geq38.5^{\circ}\text{C}$) of any duration.
- Persistent anemia (i.e., lasting >96 hours despite >2 red blood cell [RBC] transfusions).
- \geq Grade 3 transaminase (AST/ ALT) elevation.
- Any toxicity resulting in >7 held/skipped doses.
- Any other significant toxicity considered by the Investigator or the Sponsor to be dose-limiting (e.g., any toxicity considered at least possibly related to SL-901 that results in patient withdrawal during C1).

In situations in which DLTs have occurred that would prevent further dose-escalation and are severe but not life-threatening (i.e., persistent Grade 3 fever, malaise), re-evaluation of specific dose cohorts may be considered with co-administration of appropriate supportive care agents (e.g., corticosteroids, anti-depressants) concomitant with SL-901 therapy.

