4.1.1. Dose-Escalation (Part 1a)

Part 1a employs a standard 3+3 design. The SL-901 starting dose will be 20 mg on both the QD and BID schedule. The QD and BID schedules are planned to be tested in parallel, with enrollment to the current cohort for each schedule conducted on an every other patient basis. A treatment cycle is 28 days, with daily dosing throughout the cycle. The planned dose levels are summarized in [Table 5](#).

Table 5: Planned SL-901 Dose Levels in Part 1a

	Cohort						
	1	2	3	4	5	6	7
QD Dosing (mg/dose)	20	40	60	80	120	160	200
BID Dosing (mg/dose)	--	20	--	40	60	80	100
Total Daily Dose (mg/day)	20	40	60	80	120	160	200

QD = once daily, BID = twice daily

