6.4. SL-901 Dose and Administration

In both study parts, for the purposes of this study, a treatment cycle is considered to be 28 days, with daily dosing throughout the cycle.

Each SL-901 dose will be self-administered by the patient without food, either 2 hours before or 2 hours after food. The dose regimen is dependent on the patient's cohort assignment (see [Table 5](#)), and SL-901 doses should be administered at approximately the same time of day on each day of the cycle, if possible. For patients on the BID schedule, doses should be taken morning and evening at approximately the same time each day of the cycle, if possible.

On PK sample collection days, SL-901 should be administered at the study center and should be administered at (approximately) the same time of day on each day of the cycle, if possible. For patients on the BID schedule, start of PK collection must occur before the first dose of the day.

In Part 1a, the SL-901 starting dose is 20 mg on a QD schedule and a total daily dose of 40 mg on a BID schedule, as specified in [Table 5](#). The QD and BID schedules will be tested in parallel, with enrollment to the current cohort for each schedule conducted on an every other patient basis.

In Part 1b, the regimen of SL-901 will be based on the clinical experience in Part 1a.

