6.5. Rationale for the Dose(s) Selected

6.6. Dose Interruptions and Reductions

For patients that develop a clinically significant AE or unacceptable toxicity during treatment, dosing should be interrupted.

- If the toxicity resolves to the baseline level or Grade 1 within 7 days, then dosing should resume at the same dose level (during C2 and beyond, dose reduction may also be considered in consultation with the Sponsor).
- If the toxicity resolves to the baseline level or Grade 1 within 8 to 14 days, then dosing in C2 and beyond may be resumed at a reduced dose after consultation with the Sponsor.
- If the toxicity fails to resolve to baseline or Grade 1 within 14 days, then the patient should be discontinued from treatment permanently.

Specific management of unusual non-autoimmune and non-infectious toxicities known to be associated with PI3K inhibitors are summarized in [Table 6 \(Greenwell 2017\)](#).

Table 6: Management of Unusual Non-Autoimmune and Non-Infectious Toxicities

	Hypertension	Hyperglycemia	Confusion	Anxiety/ depression	Rash
Observe	BP \geq 140/90 mmHg	FG ULN-160 mg/dL	Mild disorientation	Mild symptoms	\leq 30% BSA
Hold Drug	BP \geq 200/110 mmHg	FG $>$ 160 mg/dL or NFG \geq 200 mg/dL	Limit ADL	Limit ADL	$>$ 30% BSA

Abbreviations: ADL = activities of daily living, BP = blood pressure, BSA = body surface area, FG = fasting glucose, NFG = non fasting glucose, ULN = upper limit of normal

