7.3. Analysis populations

The following analysis populations will be considered in the statistical analysis:

- DLT population: All patients receiving the complete run-in dose and at least 75% of the planned SL-901 doses in Cycle 1 and completing study assessments through C2D1, or patients discontinuing Cycle 1 due to DLT irrespective of the SL-901 dose actually received.
- Safety population: all patients enrolled into the study and who received any amount of SL-901.
- Efficacy population: all patients enrolled into the study and who received any amount of SL-901 (it corresponds to the safety population).
- Per Protocol (PP) population: all patients who received at least 1 cycle of treatment, have at least 1 post-baseline efficacy assessment, and have no major protocol violations.
- PK population: all patients who receive at least one dose of SL-901 and have at least one PK sample collected and the corresponding PK concentration. .

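### The held-dose DLT criterion counts single doses, so it is met after 8 days on QD but 4 on BID, and on QD it can place a patient with a DLT outside the DLT population

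*Protocol*

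**What the plan says.** Protocol 6.4.2 includes among the DLT criteria "Any toxicity resulting in >7 held/skipped doses". SAP 5.1 repeats it. Neither document converts the count for the BID schedule or requires the doses to be consecutive.

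Protocol 6.4 says that "a treatment cycle is considered to be 28 days, with daily dosing throughout the cycle" and that on BID "doses should be taken morning and evening". Table 5 gives amounts in mg per dose for both schedules. A dose is thus one administration.

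Three other rules bear on the count:

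- **Evaluability (Protocol 6.4.2).** "Patients are to receive at least 75% of the planned SL-901 doses in C1" and complete assessments through C2D1, "unless discontinuing due to DLT". The SAP 7.3 DLT population follows this, adds the full run-in dose, and makes an exception in these words: "or patients discontinuing Cycle 1 due to DLT irrespective of the SL-901 dose actually received".
- **Holds (Protocol 6.6).** "If the toxicity resolves to the baseline level or Grade 1 within 7 days, then dosing should resume at the same dose level". This is counted in days, with no separate provision for a hold that already counts as a DLT.
- **Discontinuation (Protocol 7.3).** A DLT is listed as a reason for which study drug may, not must, be stopped.

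Protocol 6.4.1 sets an MTD for each schedule. SAP 11.5.1 presents DLTs on the DLT population.

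**The concern.** One list of DLT criteria sets two MTDs, and identifying a regimen for further study is a primary objective. If one criterion is reached after half as much interrupted time on BID as on QD, part of any difference between the MTDs may come from the counting unit and not from tolerability. The 3+3 rule is sensitive to single events: one DLT in three patients triggers expansion, and two DLTs in a cohort end escalation on that schedule.

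This criterion also has no minimum grade. Table 6 of the protocol triggers holds by blood pressure, glucose, body surface area or limits on daily activities, so the held-dose count may be the only criterion that an event meets.

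A second issue is whether every DLT reaches the DLT table. The evaluability exception is worded for patients who discontinue, yet discontinuation after a DLT is optional.

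**Working it through.** The plan gives no figure to reproduce, so this is a direct count.

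**Inputs.** Cycle of 28 days and one or two doses a day (Protocol 6.4); criterion met at the eighth held dose (6.4.2); evaluable at 75% or more of planned Cycle 1 doses (6.4.2); same-dose resumption if the toxicity resolves within 7 days (6.6). Assumption: no BID dose is omitted on PK days; the documents state no omission.

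**Formulas.** Planned doses N = 28 × doses per day. Days to criterion = 8 / doses per day. Most doses missed while evaluable = N − 0.75N.

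| | QD | BID |
|---|---|---|
| Planned doses N | 28 | 56 |
| 75% of N | 21 | 42 |
| Most missed while evaluable | 7 | 14 |
| Days to the eighth held dose | 8/1 = 8 | 8/2 = 4 |
| Received at 8 held | 20/28 = 71.4% | 48/56 = 85.7% |
| 7-day hold, in doses | 7: not a DLT, 75.0% received | 14: a DLT, 75.0% received |
| First DLT count below 75% | 8 (71.4%) | 15 (41/56 = 73.2%) |

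The day figures are cumulative equivalents, because the doses need not be consecutive.

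**Reading the table.**

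1. On QD the cut-offs coincide: 7 held doses is 7 days, exactly 75% received, and not a DLT.
2. On BID they separate. Holds of 4 to 7 days are 8 to 14 doses: a DLT by this criterion, still evaluable (75.0% to 85.7% received), and of a length that 6.6 associates with same-dose resumption.
3. On QD, 8 or more held doses always leaves at most 71.4%. The patient has a DLT but fails the 75% rule. The exceptions in Protocol 6.4.2 and SAP 7.3 restore only those who discontinue due to DLT. On BID the same thing happens only from 15 held doses.

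**Sensitivity.** If 54 or 55 BID doses were planned, 8 held would leave 46/54 = 85.2% or 47/55 = 85.5%. The 4-day result does not change.

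**Illustration of effect.** Let p be the proportion of patients with a drug-related hold of 4 to 7 days that meets no other criterion, and assume no other DLTs. The documents give no value for p. The 3+3 rule escalates after 0/3, or after 1/3 followed by 0/3:

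P(stop) = 1 − [(1 − p)³ + 3p(1 − p)⁵]

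| p (assumed) | BID | QD |
|---|---|---|
| 5% | 1 − 0.9734 = 2.7% | 0% |
| 10% | 1 − 0.9061 = 9.4% | 0% |
| 20% | 1 − 0.7086 = 29.1% | 0% |

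**The case against.** Several points on the other side are sound and limit what can be claimed.

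- **The 75% rule on BID.** A reader might infer that the criterion contradicts the 75% rule on BID. It does not. A BID patient with 8 to 14 held doses is both evaluable and counted as a DLT. The cut-offs serve different purposes and merely fail to line up. The literal clash is on QD.
- **The hold rule.** Section 6.6 governs resumption and 6.4.2 governs classification. Other DLT criteria overlap with 6.6 in the same way on either schedule: a related Grade 3 transaminase elevation that resolves in 5 days is a DLT and also falls under same-dose resumption. Section 6.6 also counts days to resolution, not doses held. This is a misalignment to reconcile, not a contradiction.
- **Which holds are affected.** Not every 4- to 7-day BID hold is classified differently from its QD counterpart. If another criterion is met, both schedules record a DLT; if the event is not considered drug-related, neither does. The catch-all criterion for other dose-limiting toxicity narrows the group further.
- **Effect on the trial.** A reader might infer that BID escalation did stop earlier. The documents give no DLT counts and do not tie the early stop to this rule. The review committee also weighs other data (Protocol 6.4.3), and a dose below the MTD may be taken forward (4.1.2).
- **Timing.** SAP section 4 says that the study stopped early and Part 1b was not started. A protocol clarification cannot change past escalation decisions.

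The different schedules may be intended to have different hold durations, but neither document says so. None of these points removes the 8-day versus 4-day difference or the gap in the DLT population. The timing point moves the remedy towards the SAP outputs.

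**Conclusion.** The point holds in this form. The criterion is met after 8 cumulative days of held dosing on QD and 4 on BID. Where it is the sole criterion met, a drug-related hold of 4 to 7 days is a DLT on BID only. The two MTDs are then set by different standards, and BID escalation can stop earlier for a definitional reason. Whether that happened cannot be told from the documents, and the stopping probabilities above rest on assumed values of p.

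On QD, a patient with 8 or more held doses who does not discontinue fails the evaluability wording, is outside the SAP DLT population, and could be missing from the DLT table. The replacement sentence in Protocol 6.4.2 does not settle this, because it is unclear whether its exception for DLT applies to the 75% shortfall or only to early discontinuation.

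The arithmetic is exact if a dose means one administration, as Table 5 and Protocol 6.4 indicate. If a day's dosing was meant, the 4-day result disappears, but the text must say so; the QD gap remains under either meaning.

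**What to change.** 1. Reconcile Protocol 6.4.2 and 6.6 with SAP 5.1 and 7.3 so that the held-dose criterion has a stated meaning on each schedule, or state that different hold durations are intended. The choice belongs to the sponsor's clinical team; no threshold is suggested here.
2. Amend the SAP 7.3 DLT population to include every patient with a DLT, whether or not the patient discontinued.
3. In the DLT table and listing, show QD and BID separately within cohort, with the criterion that each DLT met and the number of doses and days held. SAP 11.2 reports by cohort, and cohorts 2 and 4 to 7 in Table 1 each contain both schedules. The minimum listing fields in SAP 11.5.2 include neither the criterion nor the doses held.
4. When interpreting the two MTDs, note any DLT that rests on this criterion alone.

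The cost is a text clarification and extra columns in the DLT outputs. SAP section 3 has the plan finalized before database lock, which is the natural point for items 2 and 3. If lock has passed, they can be reported as a documented change in the clinical study report.

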6.4.3. Operational Characteristics of Dose-Escalation

All dose-escalation steps and schedule recommendations will be made by a review committee, comprised of the study Investigators and Sponsor representatives, who will review the available safety and other relevant data to inform the decision. Refer to the Data Safety Review Charter (DSRC) for further details.

A sample size of at least 3 patients in each cohort, expanding to 6 patients in the event of a marginal DLT rate (33%), is a conventional approach in dose-escalation studies of investigational oncologic agents.

6.5. Rationale for the Dose(s) Selected

6.6. Dose Interruptions and Reductions

For patients that develop a clinically significant AE or unacceptable toxicity during treatment, dosing should be interrupted.

- If the toxicity resolves to the baseline level or Grade 1 within 7 days, then dosing should resume at the same dose level (during C2 and beyond, dose reduction may also be considered in consultation with the Sponsor).
- If the toxicity resolves to the baseline level or Grade 1 within 8 to 14 days, then dosing in C2 and beyond may be resumed at a reduced dose after consultation with the Sponsor.
- If the toxicity fails to resolve to baseline or Grade 1 within 14 days, then the patient should be discontinued from treatment permanently.

Specific management of unusual non-autoimmune and non-infectious toxicities known to be associated with PI3K inhibitors are summarized in [Table 6 \(Greenwell 2017\)](#).

Table 6: Management of Unusual Non-Autoimmune and Non-Infectious Toxicities

	Hypertension	Hyperglycemia	Confusion	Anxiety/ depression	Rash
Observe	BP \geq 140/90 mmHg	FG ULN-160 mg/dL	Mild disorientation	Mild symptoms	\leq 30% BSA
Hold Drug	BP \geq 200/110 mmHg	FG $>$ 160 mg/dL or NFG \geq 200 mg/dL	Limit ADL	Limit ADL	$>$ 30% BSA

Abbreviations: ADL = activities of daily living, BP = blood pressure, BSA = body surface area, FG = fasting glucose, NFG = non fasting glucose, ULN = upper limit of normal

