7.2. Dose Modifications

In Part 1a, dose modifications are not allowed in the PK Run-in Period and C1.

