7.3. Treatment Discontinuation

Study drug may be discontinued for any of the following reasons:

- Progression of disease that, in the opinion of the Investigator, precludes further study treatment. After consultation with the Sponsor, SL-901 may be continued for a patient who has met the criteria for progressive disease but in the Investigator's opinion, continues to derive benefit from study treatment.
- Occurrence of an unacceptable AE, including DLT.
- Pregnancy.
- SL-901 interruption due to study drug-related toxicity for >1 cycle (i.e., >28 days). Interruptions or delays >28 days for reasons other than AEs and/or in the setting of sustained disease control may be acceptable and are to be discussed with the Medical Monitor.
- Patient requires use of a prohibited concomitant medication or therapy.
- General or specific changes in the patient's condition unacceptable for further treatment within the study parameters, in the judgment of the Investigator.
- Non-compliance.

- Lost to follow-up.
- Patient withdrawal of consent.
- Sponsor request.
- Other.

All study procedures outlined for the End-of-Treatment (EOT) visit should be performed 30 days (± 3 days) after the last study drug dose.

In Part 1a, patients who receive <75% of the planned SL-901 doses in C1 and/or discontinue from the study before completing study assessments through C2D1 for reasons other than DLT are to be replaced.

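### The same-dose restart rule makes no exception for a DLT, and the SAP's DLT population can be read to omit a patient who had one

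*Protocol*

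**What the plan says.** **Restarting drug.** Protocol Section 6.6 calls for interruption when a clinically significant AE or unacceptable toxicity develops, then sorts patients by time to recovery:

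- Within 7 days: "If the toxicity resolves to the baseline level or Grade 1 within 7 days, then dosing should resume at the same dose level". A parenthesis adds that from C2 onward a reduction may be considered with the Sponsor.
- In 8 to 14 days: "dosing in C2 and beyond may be resumed at a reduced dose after consultation with the Sponsor".
- Not within 14 days: permanent discontinuation.

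Neither Section 6.6 nor its Table 6 mentions DLTs. Section 7.2 states: "In Part 1a, dose modifications are not allowed in the PK Run-in Period and C1". Section 7.3 opens with "Study drug may be discontinued for any of the following reasons" and lists "Occurrence of an unacceptable AE, including DLT".

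**Counting DLTs.** Section 6.4.2 sets the DLT window as the run-in and C1, and one criterion is "Any toxicity resulting in >7 held/skipped doses". For evaluability it says: "Patients are to receive at least 75% of the planned SL-901 doses in C1 and complete study assessments through C2D1", with an exemption for patients who discontinue because of a DLT. SAP Section 7.3 gives the DLT population two limbs. The first is the full run-in dose, at least 75% of C1 doses, and assessments through C2D1. The second is discontinuation of Cycle 1 because of a DLT, whatever dose was received. DLT identification is a primary endpoint (SAP 5.4.1), and DLTs are presented on this population (SAP 11.5.1).

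**The concern.** A DLT falls, by definition, in the run-in or C1, where a lower dose is not available in Part 1a. If it clears within a week, the only direction in Section 6.6 is a return to the dose that caused it. A slower recovery gets a more cautious route: a reduced dose, with the Sponsor consulted. What is at stake is the patient's exposure, and the later-cycle safety and dose-intensity data. The DLT already counted for escalation is unaffected.

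The second issue is one of analysis. Cohorts have 3 to 6 patients, so one patient lost from the DLT population changes the table materially: 1 of 3 becomes 0 of 2.

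**Working it through.** The plan gives no figure to reproduce. The check is a comparison of sections plus dose counting.

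**1. Can a DLT clear within 7 days?** Yes. Under Section 6.4.2, febrile neutropenia counts however brief it is. Grade 4 thrombocytopenia and Grade 3 or higher AST/ALT elevation carry no minimum duration. Grade 3 vomiting or diarrhea counts once it has lasted beyond 72 hours. Each can recover to baseline or Grade 1 inside a week.

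**2. What then applies in C1?** Section 6.6 triggers an interruption, and its first bullet says dosing should resume at the same level. Its optional reduction begins at C2, and Section 7.2 rules one out in C1. Section 7.3 allows stopping. Sections 6.6 and 7.3 do not refer to each other, so one recommends resuming and the other permits stopping for the same event.

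**3. Held doses against the 75% rule.** Inputs: a 28-day cycle with daily dosing (Section 6.4), giving 28 planned C1 doses on QD and 56 on BID; a DLT at more than 7 held doses; evaluability at 75% or more of C1 doses. Fraction received = (planned − held) / planned, with all held doses inside C1.

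| Schedule | Planned | 75% needs | Most that can be missed | First held-dose DLT | Fraction received then |
|---|---|---|---|---|---|
| QD | 28 | 21 | 7 | 8 doses (8 days) | 20/28 = 71.4% |
| BID | 56 | 42 | 14 | 8 doses (4 days) | 48/56 = 85.7% |

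On QD, every held-dose DLT wholly within C1 fails the 75% limb. A 14-day hold leaves 14/28 = 50.0%. On BID the patient stays evaluable up to 14 held doses (42/56 = 75.0%) and fails from 15 (41/56 = 73.2%).

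**4. Does the second limb of SAP 7.3 catch that QD patient?** If the toxicity took 8 to 14 days to clear, Section 6.6 allows a restart in C2, so treatment has not been discontinued. The patient enters only if discontinuing Cycle 1 is taken to include stopping C1 dosing and restarting in C2. A patient whose DLT follows the run-in dose and who never starts C1 has no Cycle 1 to discontinue, so is not clearly covered either.

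**5. Direct overlap on BID.** A related 4-, 5-, 6- or 7-day hold is 8, 10, 12 or 14 doses, so it is a DLT. If hold length equals time to recovery, it also falls under the 7-day same-dose bullet.

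**6. Do the two issues interact?** If drug stops after C1 day *k* with every dose taken until then, the fraction is *k*/28, which is below 75% for *k* = 1 to 20 (20/28 = 71.4%; 21/28 = 75.0%). Holding DLT patients until C2 would therefore put more of them on the second limb, so the two corrections belong together.

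**The case against.** The strongest reply is that the protocol does not force re-treatment. Section 7.3 names a DLT as a reason to stop and also allows stopping on the Investigator's judgment. The synopsis lets patients continue only until progression or unacceptable toxicity, and same-dose return requires recovery first. Weekly cohort review meetings were held (SAP 7.4.1), and the Data Safety Review Charter, which is not available here, may say more. This all stands against the stronger inference that a DLT patient must go back to the same dose. It does not remove the mismatch between a recommendation to resume and a permission to stop.

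On the population, SAP 7.3 speaks of discontinuing Cycle 1, not treatment, and can be read to include the QD patient above. In Section 6.4.2, the exclusion of DLT as a reason for replacement can likewise be read to cover patients below 75%. A DLT listing is planned as well. So a reader should not conclude that the SAP certainly drops true DLTs; the wording leaves it open. The 71.4% ceiling also needs all held doses to fall in C1. With 3 of 8 held doses in C2, the patient has 23/28 = 82.1% and is evaluable.

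A reader might also infer from the QD/BID contrast that the held-dose criterion should be counted in days. Nothing in the documents shows that days were intended. The change would double the BID threshold from more than 7 to more than 14 doses, and the only earlier human study described (Section 2.1.2.2) dosed QD. That step is not supported.

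Finally, compulsory discontinuation at the lowest level or after any run-in DLT would be a design preference, in patients with no effective standard therapy.

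**Conclusion.** Two modest points hold.

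- Section 6.6 makes same-dose resumption the default after any toxicity that recovers within 7 days, DLT or not, and this is not reconciled with Section 7.3. The consequence is for patient exposure and later-cycle data. The documents do not support a claim that it alters the DLT count, escalation or the MTD.
- Whether some true DLTs enter the SAP's DLT population depends on how one phrase is read. This affects QD patients with 8 or more doses held within C1 (at most 71.4% received) and patients with a run-in DLT who never start C1.

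The number of patients concerned cannot be derived from the documents and may be zero. The arithmetic assumes a full 28-day C1, all held doses inside it, and a toxicity judged related to SL-901.

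**What to change.** **1. Protocol 6.6 and 7.3.** Begin the 7-day bullet with: *If the toxicity is not a DLT and*. Add: *After a DLT the patient discontinues or, if the toxicity recovers to baseline or Grade 1 within 14 days and the Sponsor agrees, resumes from C2 at a reduced dose.* Where the schedule has no lower level in Table 5 (20 mg QD, 20 mg BID), leave the decision to the Investigator and Sponsor. Cross-refer the two sections.

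**2. Protocol 6.4.2 and SAP 7.3.** State that any patient with a DLT in the run-in or C1 is DLT-evaluable, whatever the doses received and whether or not treatment was discontinued, and is not replaced. Align the replacement sentences in protocol 7.3 and SAP 5.1.

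Leave the held-dose criterion in doses.

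**Cost.** Wording only, with no extra patients. A patient with a DLT on C1 day *k* who waits for C2 is off drug for 28 − *k* days, 27 at most, which is inside the 28-day interruption limit in protocol 7.3. The C1D15 PK profile is lost if the DLT comes before it. After a run-in DLT, with that dose given 3 to 7 days before C1D1, waiting for C2D1 means (3 − 1) + 28 = 30 to (7 − 1) + 28 = 34 days without drug. That passes the 28-day limit, which is itself only a permitted reason to stop, so such a case needs an explicit decision.

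The SAP reports that the study stopped early, so change 1 serves a later protocol. Change 2 can still go into the SAP if the database is not yet locked.
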